## **13.0 PHOTOGRAPHY**

Standardized photographs will be taken of the treatment area. If the photograph is located on the face the subject will be asked to remove jewelry and make up and lotions prior to each photo session. Photographs will be taken with an appropriate high-resolution digital camera. Camera settings

(lighting, distance, background, polarization, etc.) will be reproduced at each visit, so that photographs are suitable for comparison. Photographs will be taken of the treatment area for study purposes. If the subject does not wish to have their photographs taken, they cannot be in the study.

#### 14.0 ADVERSE REACTIONS DEFINITIONS AND REPORTING REQUIREMENTS

All adverse events that occur, starting from the time of the first treatment, will be recorded in the source documents and Case Report Forms (CRF).

Adverse Events (AE) occurring will be captured and followed until the condition resolves, stabilizes, is otherwise explained, or the subject is lost to follow-up. Subjects will be instructed that they may contact the Investigator at any time throughout the course of the study.

The Investigator and/or designated study staff will review each event and assess its relationship to the study device (not related, unlikely, possible, probable, and highly probable). The following definitions will be used for rating relationship to the PotenzaTM treatments:

- Not related The event is clearly related to other factors such as the subject's clinical state, therapeutic interventions, or concomitant medications administered to the subject.
- Unlikely The event was most likely produced by other factors such as the subject's clinical state, therapeutic interventions, or a concomitant medication administered to the subject; and does not follow a known response pattern to the investigational product.
- Possible The event follows a reasonable temporal sequence from the time of investigational product administration; **and/or** follows a known response pattern to the study sampling sessions; **but** could have been produced by other factors such as the subject's clinical state, therapeutic interventions, or concomitant medications administered to the subject.
- Probable The event follows a reasonable temporal sequence from the time of investigational product administration; **and** follows a known response pattern to the investigational product; **and** cannot be reasonably explained by other factors such as the subject's clinical state, therapeutic interventions, or concomitant medications administered to the subject.
- Highly Probable The event follows a reasonable temporal sequence from the time of investigational product administration; and follows a known response pattern to the investigational product; and cannot be reasonably explained by other factors such as the subject's clinical state, therapeutic interventions, or concomitant medications administered to the subject; and either occurs immediately following investigational product administration, or improves on stopping the investigational product, or reappears on repeat exposure, or there is a positive reaction at the application site.

Each adverse event reported will be graded on a 3-point severity. Using the following definitions for rating severity will be used:

- Mild easily tolerated, causing minimal discomfort, and not interfering with normal everyday activities.
- Moderate sufficiently discomforting and may interfere with normal everyday activities.
- Severe incapacitating and/or preventing normal everyday activities.

A Serious Adverse Event (SAE) is any adverse device experience that results in any of the following outcomes: death, a life-threatening adverse device experience, in-patient hospitalization or prolongation of hospitalization, a persistent or significant disability/incapacity, or a congenital anomaly/birth defect. Important medical events that may or may not result in death, be life-threatening, or require hospitalization may be considered a serious adverse device experience when, based upon appropriate medical judgment, they may jeopardize the subject or subject may require medical or surgical intervention to prevent one of the outcomes listed in this definition

If any of the above adverse events are serious as defined by the FDA Code of Federal Regulations (CFR), Title 21, special procedures will be followed. All serious adverse events will be reported within 24 hours of acknowledgment to the Sponsor whether or not the serious events are deemed sampling session related. All serious event reporting will adhere to 21 CFR part 812 and the IRB will be notified accordingly.

The SAE information will be entered into the database and a desk copy of the complete SAE report will be submitted to the study file.

Adverse events, whether serious or non-serious, will be followed until the condition is resolved, stabilized, otherwise explained or the subject is lost to follow-up. Adverse events will be captured throughout the study and where appropriate, medical tests and examinations will be performed to document the resolution of event(s). Outcomes may be classified as resolved, improved, unchanged, worse, fatal, unknown or lost to follow-up. Following the resolution of any study-associated adverse events there will be no further adverse event reports for that subject.

Report	Submit To	Description/Constraints
Adverse Events, Unanticipated Adverse Device Effect	IRB and Sponsor	If an unforeseen complication is determined to be an unanticipated adverse device effect, the investigator's report must be submitted within 10 working days after the investigator first learns of the effect.
Serious Adverse Events	IRB and Sponsor	The sponsor must be notified within 24 hours of serious adverse events. The IRB must be notified within 10 working days of serious adverse events as defined by FDA guidelines.

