## **1.2 Objectives**

- 1. Primary Objectives:
  - Assessment of safety of the study device through the collection of side effects throughout the study.
  - Assessment of the efficacy of the study device through Investigator and subject satisfaction.
  - Evaluation of baseline photographs compared to post treatment images.
- 2. Assessments:
  - Treatment discomfort evaluation
  - Subject treatment experience questionnaire
  - Clinician ease of use questionnaire
  - Clinician and subject satisfaction questionnaire
  - Treatment area photograph blinded evaluation
  - Baseline and short-term histological tissue response as seen in biopsies.

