#### **2.5 Informed Consent Process and Enrollment**

Subjects will be asked to review the pre and post treatment instructions prior to signing the informed consent and their involvement in the study. Subjects who sign the informed consent will be screened to confirm eligibility and if eligible, will be assigned a subject identification number. Subjects will be de-identified through their subject identification number, which will be stored in a secure location. Subject identification numbers will be generated chronologically and assigned only to subjects who have met all the study selection criteria and have signed the informed consent form. The informed consent will be obtained prior to a subject's involvement in any study related procedures. A subject will be considered enrolled in the study once they have signed the informed consent form. Employees of the Sponsor will be required to sign both the main informed consent form as well as an employee consent form.

[figure not shown]

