#### **2.7 Treatment Procedures**

- The treatment area will be identified and may be marked with a surgical marker.
- Anesthesia (such as a topical or local), air cooling, and/or Nitronox will be used at the discretion of the Investigator.

(UNO(URE

- A neutral pad will be placed in an area determined by the Clinician to maintain standard energy settings and requires less power from the device during the treatment.
- Test spots may be performed prior to the first treatment. Test spots may be performed prior to the first treatment. It will follow a similar procedure to treatment but only in an inconspicuous place, such as behind the ear, in an area no larger than 2in x 2in.
- The tip will be placed in contact with the skin.
- The entire defined treatment area will then be treated as instructed by the Operator's Manual.
- Parameters may be adjusted throughout the treatment and will determined by the Clinician.
- Subjects will be asked to report the general level of treatment discomfort/pain on a scale of 0 (none) to 10 (maximum intolerable pain).
- Photographs may be taken during treatment.
- Subjects may receive up to 5 treatments every 4 weeks (+/- 2 weeks) which will be determined by the Investigator.
- The additional treatments will follow the same procedure.

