#### Adverse Events Pertaining to Anesthesia:

Topical anesthesia, such as but not limited to; EMLA, LMX and Lidocaine/Tetracaine, or a local anesthetic will be used. The most common side effects for most anesthetics include redness, blanching, swelling and application site reaction.

Less common side effects include; large swellings that look like hives on the skin or in the mouth or throat. Pain, burning, paleness and altered temperature sensation. Subjects may be allergic to the contents of any anesthetic which may cause allergic-type reactions including anaphylactic symptoms and life-threatening or less severe asthmatic episodes in certain susceptible people.

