#### 2.16.3 Patient Populations

Interim results may be collected and reported. All data will be analyzed at the end of the study. The primary analysis will be performed by the intention-to-treat approach. Everyone who begins the treatment is part of the study whether he or she completes the study or not. Additional perprotocol analysis may also be performed on subjects who complete the entire clinical trial according to the protocol. The most appropriate method of handling missing values will be chosen based on the individual trial goals, endpoints and context.

The analysis of demographic, medical history, and efficacy variables will be based on all patients who are randomized and receive at least one treatment. The analysis of safety data will be based on all patients who are randomized, receive at least one treatment, and have at least some safety data.

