#### 2.16.6 Analysis of Safety Variables

Safety will be assessed through the degree of pain/discomfort related to the procedure (universal pain scale) and the collection of Adverse Events throughout the course of the study. For each treatment group these variables will be summarized. The summaries will include the number and percent of patients for each outcome. No statistical comparisons will be performed for any of these variables.

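### The start of adverse event recording is contradictory and its only explicit form leaves out device test spots, while the safety set drops any test-spot reactor who is never treated

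*Combined protocol and SAP*

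**What the plan says.** **Start of recording.** Section 14.0 opens with "All adverse events that occur, starting from the time of the first treatment, will be recorded in the source documents and Case Report Forms". Further on, the same section says "Adverse events will be captured throughout the study and where appropriate, medical tests and examinations will be performed", with no start point. Section 2.16.6 bases the safety analysis on "the collection of Adverse Events throughout the course of the study", and the first primary objective in 1.2 is "Assessment of safety of the study device through the collection of side effects throughout the study".

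**Exposure before treatment.** Section 2.7 states "Test spots may be performed prior to the first treatment". It describes the spot as done much like a treatment, on an area of at most 2in x 2in. Anesthesia, air cooling and Nitronox are at the investigator's discretion. Section 2.15 accepts that an anesthetic can cause "allergic-type reactions including anaphylactic symptoms and life-threatening or less severe asthmatic episodes".

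**Schedule.** In 2.13 the adverse event row is blank at Visit 1 and marked at the treatment visits, calls and follow-up visits.

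**Who is counted.** Section 2.5 says "A subject will be considered enrolled in the study once they have signed the informed consent form". Section 2.16.3 restricts the safety analysis to patients who "receive at least one treatment, and have at least some safety data". Section 12.0 says that data gathered before a withdrawal will go into the analysis.

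**The concern.** Two separate rules bear on the same subject: one decides whether an event is written down, the other whether the person is counted.

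Take a subject who has consented, has a test spot, develops a burn or pigment change there, and is not treated. Under the opening rule of 14.0 the event comes before recording starts. Under 2.16.3 the subject is outside the safety set. Even if the site does record the event, the safety summary has no place for it.

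This exclusion would depend on the outcome. The people lost would be those who reacted at their first contact with the device, so the summary could only move toward a cleaner profile. An acceptable side effect profile is part of the success rule in 2.16.1, and 3.3 names the safety profile as one of the two device risks. Replacement of withdrawn subjects under 2.12 could also put a treated subject in the reactor's place.

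**Working it through.** The plan gives no test-spot reaction rate and no figure for this point, so there is nothing to reproduce. The check is a comparison of the text, followed by an illustration.

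**1. When does recording start?** Section 14.0 (opening): first treatment. Section 14.0 (later paragraph), 2.16.6 and 1.2: throughout the study. Section 2.5 puts a subject in the study from consent, so the second group of statements covers a test spot and the first does not. Only the first names a start.

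**2. Can a test spot fall where no assessment is scheduled?** Section 2.7 places it before the first treatment without naming a visit. The footnote in 2.13 says that screening may coincide with the first treatment visit and also that it must come at least 30 days earlier. A separate earlier visit is therefore possible, and its adverse event cell is blank.

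**3. Is a never-treated reactor in the safety set?** Section 2.16.3 requires at least one treatment. The documents do not say that a test spot counts as a treatment, and 2.7 sets it apart from the first treatment. As written, the answer is no. Section 12.0 points the other way for a subject who withdraws or is removed after the test spot, and the two are not reconciled. (Section 2.16.3 also requires randomization, which this open-label design does not describe. That is a separate matter.)

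**4. Illustration.** Inputs: N = 120 enrolled (2.16.2). Assumed: all 120 have a test spot, k react and are never treated, and no treated subject has the same reaction.

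- Rate among all exposed = k/120, with an exact (Clopper-Pearson) 95% interval.
- Rate in the written safety set = 0/(120 − k), with upper 95% limit 1 − 0.025^(1/(120 − k)).

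| k (assumed) | All exposed | Exact 95% CI | Written safety set | Upper limit |
|---|---|---|---|---|
| 1 | 1/120 = 0.83% | 0.02% to 4.56% | 0/119 = 0% | 3.05% |
| 2 | 2/120 = 1.67% | 0.20% to 5.89% | 0/118 = 0% | 3.08% |
| 3 | 3/120 = 2.50% | 0.52% to 7.13% | 0/117 = 0% | 3.10% |
| 6 | 6/120 = 5.00% | 1.86% to 10.57% | 0/114 = 0% | 3.18% |

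Each such reactor takes 1/120 = 0.83 percentage points off the reported incidence.

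**5. If similar events also occur after treatment.** With m affected treated subjects, the gap is (m + k)/120 − m/(120 − k) = (k/120) × (1 − m/(120 − k)). This is never negative. For k = 3 and m = 3 (both assumed), it is 6/120 − 3/117 = 5.00% − 2.56% = 2.44 points, against 2.50 points when m = 0. Later events change the gap little and do not reverse it.

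**The case against.** A reader might infer that test-spot reactions are certain to go unrecorded. The documents do not support that. Three statements say collection runs throughout the study, and the 24-hour serious-event rule in 14.0 has no first-treatment limit, so a severe reaction is the one least likely to be lost. What stands is that a site has two rules, and the one with a stated start leaves the test spot out.

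Test spots are optional and are described under treatment procedures. If one is done at a treatment visit, that visit's assessment may catch the reaction. In the biopsy portion (up to 6 subjects), the test-spot area is biopsied on the day of treatment and Biopsy #1 has an assessment. This narrows the recording gap. It does not help a subject who is never treated.

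The anesthetic part is weaker. Its use at a test spot is inferred from the similarity to treatment, and anesthetic given at a treatment visit is followed by a scheduled assessment. It matters only when a subject reacts and treatment then does not go ahead.

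The chain also needs a decision not to treat, and no section says that a test-spot reaction leads to one. The documents do not show that this will happen, only that the plan loses the subject if it does.

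A reader might also infer that the reported upper limit would exclude the real rate. In the illustration this begins only at 4 reactors (4/120 = 3.3% against an upper limit of 3.1% for 0/116). Even there, 3.3% is an observed proportion whose interval, 0.9% to 8.3%, overlaps 0% to 3.1%.

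Finally, safety is summarised without comparisons, the success rule has no numeric threshold for side effects, and the study calls itself a feasibility study. So no change in the study's conclusion can be shown. The definition of the primary safety data is still at fault.

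**Conclusion.** The point holds in two parts. First, the start of adverse event recording is contradictory, and its only explicit form leaves out optional test spots. Second, the safety set in 2.16.3 excludes an enrolled subject who reacts to a test spot, or to anesthetic given beforehand, and is never treated, whether or not the event is recorded. Apart from the conflicting sentence in 12.0, nothing in the documents offsets the second part.

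The bias runs toward a cleaner profile. Its size is unknown. The illustrated range, 0.8% to 5.0% among all exposed against 0% in the written safety set for 1 to 6 reactors, rests on three assumptions: every subject has a test spot, the reactors are never treated, and no similar event follows treatment. It also takes a test spot not to count as a treatment, which the documents leave unstated.

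**What to change.** - **14.0:** start recording at consent or at the first study exposure, naming test spot and anesthetic. Reconcile the opening sentence with the later paragraph of 14.0, with 2.16.6 and with 1.2.
- **2.13:** mark an adverse event assessment at any visit where a test spot is done, Visit 1 included.
- **2.16.3:** define the safety set as all subjects exposed to the device, test spot included, or to study anesthetic. List separately those not treated further. This also removes the conflict with 12.0.

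Most of the cost is wording. The safety profile may look slightly less favourable. Follow-up contacts in 2.9 are tied to treatments, so catching a delayed reaction, such as pigment change, in a never-treated subject may need a follow-up call.

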## **2.8 Post Treatment Procedures**

- Adverse events will be documented after treatment.
- Photographs may be taken post treatment.
- Clinician ease of use and subject treatment experience questionnaires may be performed.
- The following post treatment instructions will be reviewed:
  - Be careful not to expose area of treatment to external stimulation for at least 2 days after treatment.
    - Avoid ultraviolet rays and apply sunscreen.
    - Do not to scrub the skin or exfoliate for several days after treatment.
  - Refrain from high intensity exercise (such as running, weightlifting, aerobics), hot bath or saunas that may cause increase in skin temperature for 5 days after treatment.
  - Refrain from drinking alcohol or taking medicine that interferes with blood coagulation such as aspirin for 2 weeks after treatment.
  - If heat sensation or erythema (redness) after treatment is bothersome, use an ice pack to the treated area at home.
  - If the skin in the treatment area feels tight or dry, apply plenty of moisturizing cream, such as Neutrogena.
  - After the procedure, inflammation or edema (swelling) may block the pores and acne can temporarily worsen (about 7 days). If acne worsens, do not pick or squeeze as pigmentation changes may occur.
  - Sleep in a semi reclined position for the first 2-3 nights to minimize facial swelling.
  - Apply soothing facial mask as needed.

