## 2.9 Follow Up

- All subjects may receive a 24 hour phone call or attend a visit post each treatment and will receive a phone call or attend a visit 1 week (2-10 days) after each treatment to record side effects.
- The study subjects are required to return to the investigative site for a follow-up evaluation at 30 days post last treatment.

(UNO(URE

- Subjects may be asked to return for an optional follow up visit 90 days post last treatment.
- Photographs will be taken, subject and physician questionnaires will be performed, and adverse events will be documented at all follow up visits.
- Some subjects may have an incomplete response or no response by the end of the study. At the end of the study, treatments using an FDA approved/cleared treatment method may be discussed with the subject and obtained at the cost of the subject.

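### Section 14.0, read literally, ends a subject's adverse event reports once a study-associated event resolves, although the protocol otherwise collects events throughout the study

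*Combined protocol and SAP*

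**What the plan says.** The sentence at issue closes the follow-up paragraph of section 14.0: "Following the resolution of any study-associated adverse events there will be no further adverse event reports for that subject". It sets no visit or end-of-study limit and makes no exception for new or unrelated events.

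Other text keeps collection open:

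- Same paragraph of section 14.0: "Adverse events will be captured throughout the study".
- Opening of section 14.0: "All adverse events that occur, starting from the time of the first treatment, will be recorded in the source documents".
- Section 1.2, first primary objective: safety is assessed through "collection of side effects throughout the study".
- Section 2.8: "Adverse events will be documented after treatment".
- Section 2.9: each subject "will receive a phone call or attend a visit 1 week (2-10 days) after each treatment to record side effects". Adverse events are also to be documented whenever a follow-up visit takes place.
- Section 2.13: the adverse event assessment is marked at the treatment visits, the calls and the follow-up visits.
- Section 2.16.6: the safety analysis rests on collection over the whole study and reports the number and percent of patients for each outcome.

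The end point for following an event is stated in more than one way. Section 2.15 gives resolution only. Section 14.0 says that events "will be captured and followed until the condition resolves, stabilizes, is otherwise explained, or the subject is lost to follow-up". Section 12.0 closes data collection at withdrawal.

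**The concern.** Safety is the first primary objective, and section 2.16.1 makes an acceptable side-effect profile part of the success rule. If a site applied the sentence as written, a subject whose early redness had resolved would generate no further adverse event reports, with up to 4 treatments (5 − 1) still to come. Section 2.15 also lists burns, pigment changes, infection and scarring as possible. If such an event was non-serious and first appeared after the stop, it could be left out of that type's percentage. With 5 centers, sites could also read the sentence differently.

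A smaller issue lies alongside it. Because the follow-up end points differ, it is unclear how an event that is still open at withdrawal should be handled.

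**Working it through.** The plan gives no figure to reproduce and no event rates. The check is a comparison of text, with one piece of timing arithmetic.

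**1. Scope of the sentence.** The stop is defined by subject. Section 14.0 uses the word 'reported' for adverse events in general when it introduces severity grading, so 'reports' need not mean only submissions to the IRB or sponsor. On the literal reading, an event that starts after the stop is covered by the recording and capture rules but barred by the reporting rule. Both cannot be followed as written.

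**2. When the stop could fall.**

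- Inputs: erythema and tingling disappear within 48 hours (section 2.15); up to 5 treatments, every 4 weeks with a window of 2 weeks either way (section 2.7).
- Shortest gap between treatments: 4 − 2 = 2 weeks = 14 days.
- Expected duration of these events: 48 hours = 2 days.
- Since 2 < 14, a subject whose only events after treatment 1 are erythema or tingling would reach the stop before treatment 2. This holds whether 'any' is taken to mean one event or all events so far.

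**3. Effect on the section 2.16.6 summaries if the stop were applied.**

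- Percent of patients with at least one study-associated event: no change, because the stop is triggered only after such an event has been captured.
- Percent with a type already recorded for that subject: no change from a repeat of the same type.
- Percent with a new type, or with an unrelated event arising after the stop: understated. With at most 120 subjects enrolled (section 2.1), each subject missed lowers that type's figure by at least 1/120 = 0.83 percentage points. This is the effect per missed subject; the number of subjects missed is unknown and may be zero.

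**4. Events outside the problem.** Section 14.0 has a separate rule for serious events: "All serious adverse events will be reported within 24 hours of acknowledgment to the Sponsor", whether or not they are considered related. Its table gives unanticipated device effects their own deadline of 10 working days. What remains is other, non-serious events.

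**5. Follow-up end points.** Section 14.0 states its end points twice, and the two statements agree. Section 2.15 does not allow the additional ones. For an event open at withdrawal, sections 2.15 and 14.0 imply continued follow-up, while section 12.0 collects nothing more.

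**The case against.** The strongest reply is that the sentence is ambiguous and has harmless readings.

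- **It only closes the resolved event.** This is sensible, but the text speaks of the subject, not the event.
- **Only IRB and sponsor submissions end.** The table that follows directly is about submissions, and the paragraph uses a different verb for capture. However, the table lists only serious events and unanticipated device effects, which have reporting rules of their own, so this reading creates a different conflict.
- **It is a close-out at the end of participation.** The paragraph moves from follow-up to capture to outcome and only then to this sentence, so it may simply end follow-up that runs past the last visit. On that reading nothing is lost during the study. The reading is plausible, but the text does not state it.

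A second reply is that collection is protected elsewhere. A site would have to let one sentence override sections 2.8, 2.9, 2.13 and 14.0's own capture rule. Section 2.13 prompts the assessment, section 2.15 provides sponsor review and section 5.0 provides case report form review. This stands, and it limits the practical risk. The review in section 2.15 covers documented events, however, so it cannot recover one that was never recorded.

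On the end points, section 12.0 does ask withdrawing subjects for a final follow-up visit, and section 14.0 provides outcome categories for unresolved events. That narrows the secondary issue but does not remove the difference from section 2.15.

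A reader might infer that the trial will under-count adverse events, or that serious event reporting stops. The documents support neither. Assessments stay scheduled at every contact, and serious events have a separate 24-hour rule.

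**Conclusion.** The point holds as a conflict in wording that should be fixed. Read literally, the sentence contradicts capture throughout the study, and the protocol's own timings show that the stop could take effect before treatment 2. The exposure is confined to new types of non-serious event, and unrelated non-serious events, that arise after an earlier study-associated event has resolved.

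The size cannot be estimated. It is zero if sites follow sections 2.9 and 2.13. Otherwise it depends on event rates and site behaviour that the documents do not give. The conclusion rests on the literal reading being one that a site could reasonably adopt; it does not assume that any site has done so.

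The difference between sections 2.15, 14.0 and 12.0 on follow-up end points is real but secondary.

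**What to change.** 1. Replace the last sentence of the follow-up paragraph in section 14.0 with: *A resolved event is closed; new or recurrent events continue to be recorded and reported throughout the subject's participation.*
2. In section 2.16.6, summarise events through Visit 8 for all subjects and show events found at Visit 9 separately. Visit 9 is optional, so otherwise some subjects would be observed for about 30 days after the last treatment and others for about 90.
3. Reconcile sections 2.15, 14.0 and 12.0 to one follow-up end point, and state how it applies to events open at withdrawal. The choice of end point is for the sponsor and investigators.

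The cost is one replaced sentence and short wording changes, made by amendment with IRB approval under section 21.0. No visit or assessment is added, because section 2.13 already schedules the adverse event assessments. Reported counts would rise only where a site had stopped early.
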